7.4.2.2.1. Secondary Endpoint 2 - Main Analysis

Vaccination Status

If a participant received at least one dose of Trumenba and at least one dose of MenACWY vaccine will be considered as vaccinated (exposed population).

Analysis

We will assess chlamydial infection that occurred between 14 days after zero time and till end of the study period. The analysis will be performed same as in Section 7.2.1.1.

7.4.2.3 Secondary Endpoint 3 - Effectiveness of Trumenba against chlamydial infection.

VE calculated as 1 minus the hazard ratio for chlamydial infection between the recipients (aged 15-30 years) of both Trumenba (at least one dose) and MenACWY (at least one dose) vaccines and the recipients (aged 15-30 years) of MenACWY vaccine only multiplied by 100 adjusted for potentially confounding variables.

7.4.2.3.1. Secondary Endpoint 3 - Main Analysis

Vaccination Status

If a participant received at least two doses of Trumenba and at least one dose of MenACWY vaccine will be considered as vaccinated (exposed population).

Analysis

We will assess chlamydial infection that occurred between 14 days after zero time and till end of the study period. The analysis will be performed as written in the Section 7.2.1.1.

7.2.3.4. Exploratory Endpoint 1 – Effectiveness of Trumenba against gonococcal infection.

VE calculated as 1 minus the hazard ratio for gonococcal infection between the recipients (aged 16-23 years) of both Trumenba (at least two doses) and MenACWY (at least one dose) vaccines and the recipients (aged 16-23 years) of MenACWY vaccine only multiplied by 100, adjusted for potentially confounding variables.

PFIZER CONFIDENTIAL CT24-WI-GL03-RF03 2.0 Non-Interventional Statistical Analysis Plan For Secondary Data Collection Study 01-Jun-2020 Page 15 of 28

7.2.3.4.1. Exploratory Endpoint 1 - Main Analysis

Vaccination Status

If a participant received at least one dose of Trumenba and at least one dose of MenACWY vaccine will be considered as vaccinated (exposed population).

Analysis

We will assess gonococcal infection that occurred between 14 days after zero time and till end of the study period. The analysis will be performed as written in the Section 7.2.1.1.

7.2.3.5. Exploratory Endpoint 2 – Effectiveness of trumenba against gonococcal infection.

VE calculated as 1 minus the hazard ratio for gonococcal infection between the recipients (aged 15-30 years) of both Trumenba (at least one dose) and MenACWY (at least one dose) vaccines and the recipients (aged 15-30 years) of MenACWY vaccine only multiplied by 100 adjusted for potentially confounding variables.

7.2.3.5.1. Exploratory Endpoint 2 - Main Analysis

Vaccination Status

If a participant received at least one dose of Trumenba and at least one dose of MenACWY vaccine will be considered as vaccinated (exposed population).

Analysis

We will assess gonococcal infection that occurred between i) 14 days after zero time and 365 days ii) 14 days after zero time and 730 days, iii) 14 days after zero time and 1095 days, and iv) 14 days after zero time and till end of the study period. The analysis will be performed as written in the Section 7.2.1.1.

PFIZER CONFIDENTIAL CT24-WI-GL03-RF03 2.0 Non-Interventional Statistical Analysis Plan For Secondary Data Collection Study 01-Jun-2020 Page 16 of 28

7.4.3 Summary of Analyses

Outcome	Analysis Set	Supports	Subgroup	Statistical Method	Covariates/Strata	Missing Data
		Protocol				
		Objective				
		Number				
Gonococcal and chlamydial infections	All patients	All	Gender, age group, and US region, if required	Cox proportional hazard regression	Demographic characteristics, if required.	Excluded
Time to event, days	All patients	All	Same as above	Cox proportional hazard regression	Same as above	Excluded

PFIZER CONFIDENTIAL CT24-WI-GL03-RF03 2.0 Non-Interventional Statistical Analysis Plan For Secondary Data Collection Study 01-Jun-2020 Page 17 of 28

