2.2.3 Exploratory Objectives

- To examine the effect of at least one dose of Trumenba on gonococcal infection in adolescents and young adults of 16-23 years in the United States
- To examine the effect of at least one dose of Trumenba on gonococcal infection in adolescents and young adults of 15-30 years in the United States at 12 months, 24 months, 36 months and 48 months following the index vaccination

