3 HYPOTHESES AND DECISION RULES

PFIZER CONFIDENTIAL CT24-WI-GL03-RF03 2.0 Non-Interventional Statistical Analysis Plan For Secondary Data Collection Study 01-Jun-2020 Page 6 of 28 This is an exploratory study, thus no hypothesis will be tested. There will be more than 500,000 individuals in which approximately 15% will be the experimental group. Assming a total of 500,000 subjects, and the probability of failure in the experimental group over the maximum time period of the study is 0.0036 and the probability of failure in the control group over the maximum time period of the study is 0.0048. This provides a power of 94% assuming a hazard ratio of 80% (20% vaccine effectiveness) and at an alpha of 0.05. The calculation was made using "powerSurvEPI" package under RStudio (Version 1.1.453).

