3.2 STATISTICAL DECISION RULES

The alpha level will be 0.05, 2-sided. No adjustments for multiple comparisons will be made.

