8.3 TABLES – EXPLORATORY ENDPOINTS

		Exposed cohort				Non-E	Exposed co	ohort	Unadjusted	Adjusted
	No. of persons	No. of cases	Person- years	Incidence/ 100,000/year	No. of persons	No. of cases	Person- years	Incidence/ 100,000/year	VE (95% CI)	VE (95% CI)
≥ 1 dose of T	rumenba	1	1	1	1	r	1	1	I	
Gonococcal infection	XX	xx	xxxx	XX.XX	XX	xx	xxxx	XX.XX	xx (xx, xx)	XX (XX, XX)
Gonococcal infection only	xx	XX	xxxx	xx.xx	xx	XX	xxxx	xx.xx	xx (xx, xx)	XX (XX, XX)
Chlamydial infection	XX	XX	xxxx	xx.xx	XX	XX	xxxx	xx.xx	XX (XX, XX)	xx (xx, xx)
Chlamydial infection only	xx	xx	xxxx	xx.xx	xx	XX	xxxx	xx.xx	XX (XX, XX)	xx (xx, xx)
≥ 2 doses of $[$	[[] Frumenb	a								
Gonococcal infection	xx	xx	xxxx	xx.xx	XX	XX	xxxx	xx.xx	xx (xx, xx)	xx (xx, xx)
Gonococcal infection only	xx	XX	xxxx	xx.xx	xx	XX	xxxx	XX.XX	xx (xx, xx)	XX (XX, XX)
Chlamydial infection	XX	XX	xxxx	xx.xx	XX	xx	xxxx	xx.xx	XX (XX, XX)	$\begin{array}{c} \mathbf{x}\mathbf{x}\\ (\mathbf{x}\mathbf{x},\mathbf{x}\mathbf{x}) \end{array}$
Chlamydial infection only	xx	xx	xxxx	XX.XX	xx	xx	xxxx	XX.XX	xx (xx, xx)	xx (xx, xx)

Table 3.1. Effectiveness of Trumenba in 16-23 Years Old

VE calculated as 1 minus the hazard ratio for gonococcal infection between exposed and non-exposed cohort, multiplied by 100

PFIZER CONFIDENTIAL CT24-WI-GL03-RF03 2.0 Non-Interventional Statistical Analysis Plan For Secondary Data Collection Study 01-Jun-2020 Page 21 of 28

Table 3.2 Effectiveness of Trumenba in 15-30 Years by Year of Follow-up Among Participants received ≥1 dose of Truumenba

		Me	enACWY	only	T	RUMEN	NBA and N	MenACWY	Unadjusted VE		Adjusted VE	
	No. of persons	No. of cases	Person- years	Incidence/ 100,000/year	No. of persons	No. of cases	Person- years	Incidence/ 100,000/year	VE	95% CI	VE	95% CI
At 12 months	of follow	v-up			1	1	1		1	1		
Gonococcal infection	XX	xx	xxxx	xx.xx	XX	XX	XXXX	XX.XX	xx	xx, xx	XX	xx, xx
Chlamydial infection	XX	XX	xxxx	XX.XX	XX	XX	XXXX	XX.XX	xx	xx, xx	XX	xx, xx
At 24 months	of follow	v-up										
Gonococcal infection	XX	XX	xxxx	XX.XX	xx	XX	XXXX	XX.XX	xx	xx, xx	XX	xx, xx
Chlamydial infection	xx	XX	xxxx	xx.xx	xx	XX	xxxx	XX.XX	xx	xx, xx	XX	xx, xx
At 36 months	of follow	v-up			1	I.				1		
Gonococcal infection	XX	XX	xxxx	xx.xx	XX	XX	XXXX	XX.XX	xx	xx, xx	XX	xx, xx
Chlamydial infection	XX	XX	xxxx	XX.XX	XX	XX	XXXX	XX.XX	xx	xx, xx	XX	xx, xx
At 48 months	of follow	v-up										
Gonococcal infection	XX	XX	xxxx	XX.XX	XX	XX	XXXX	XX.XX	XX	xx, xx	XX	xx, xx

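### The 12-, 24-, 36- and 48-month analyses use nested windows that all start at day 14, so if effectiveness changes over time they do not give the effect at each time or in each year

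*SAP*

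**What the plan says.** The exploratory objective in SAP 2.2.3 is to examine the effect "at 12 months, 24 months, 36 months and 48 months following the index vaccination". Protocol 8.1.3 names the same four times.

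The analysis in SAP 7.2.3.5.1 defines four windows. The first ends at day 365, the next two are "14 days after zero time and 730 days, iii) 14 days after zero time and 1095 days", and the fourth runs from day 14 to the end of the study. Protocol 9.7 gives the same four and dates the last one 31 December 2022. SAP 5.3.2 also describes periods that all run from zero time, but ends the fourth at 48 months.

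Each window is analysed as in SAP 7.2.1.1: a Cox model with one coefficient for vaccine, hence one hazard ratio. That section has proportionality checked for every independent variable. A covariate that fails is dropped from the model and used for stratification.

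The results go into Table 3.2 (SAP 8.3), headed "Effectiveness of Trumenba in 15-30 Years by Year of Follow-up", with rows for 12, 24, 36 and 48 months of follow-up.

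**The concern.** The 24-month window contains the whole 12-month window, the 36-month window contains both, and so on. A single hazard ratio fitted to such a window averages over everything since day 14. Set beside an objective about the effect at given times and a heading that speaks of years, the figures invite a reading that they cannot bear. This is also the only planned adjusted analysis that could speak to waning or durability. If protection faded, a later row could show a positive VE carried over from the first year. If protection built up slowly, a later row would understate it.

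**Working it through.** **1. The plan's own figure.** SAP 3 gives one power statement, for the whole follow-up. Its inputs are "Assming a total of 500,000 subjects", of whom "approximately 15% will be the experimental group" (75,000 exposed, 425,000 reference), and failure probabilities of 0.0036 (exposed) and 0.0048 (reference).

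- Events: 75,000 × 0.0036 + 425,000 × 0.0048 = 270 + 2,040 = 2,310.
- Allocation ratio: k = 75,000/425,000 = 0.1765.
- Freedman-type power at HR 0.80, two-sided 0.05: Φ(√(0.1765 × 2,310) × 0.20/(0.1765 × 0.80 + 1) − 1.96) = Φ(20.19 × 0.20/1.141 − 1.96) = Φ(1.58) = 94.3%.

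This reproduces the stated 94%. It applies to the overall comparison only. No figure is given for the 12- to 48-month windows.

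**2. What a nested window estimates.** For a rare outcome the single hazard ratio is close to a weighted mean of the yearly hazard ratios:

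VE through year J = 1 − Σ wⱼ(1 − VEⱼ)/Σ wⱼ, for j = 1 to J,

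where wⱼ is the relative number of events expected in year j at the reference hazard. If VE is the same every year, the weights cancel and each window returns that VE.

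**3. Illustration with changing VE.** The documents give no waning pattern. Assume true VE of 40, 20, 0 and 0% in years 1 to 4. The weights are also assumptions. The two Cox rows solve the expected partial-likelihood score, with a constant reference hazard of 0.0048/7 per year and up to seven years of follow-up.

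| Spread of events | 12 m | 24 m | 36 m | 48 m |
|---|---|---|---|---|
| True VE in that year | 40 | 20 | 0 | 0 |
| Equal weights 1, 1, 1, 1 | 40 | 30 | 20 | 15 |
| Cox, 20% disenrolment per year | 40 | 30.9 | 22.7 | 18.7 |
| Declining weights 1, 0.75, 0.5, 0.3 | 40 | 31.4 | 24.4 | 21.6 |
| Cox, 40% disenrolment per year | 40 | 32.3 | 26.2 | 23.5 |
| Late weights 1, 1.5, 2, 2 | 40 | 28 | 15.6 | 10.8 |

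For example, declining weights at 48 months give (1 × 40 + 0.75 × 20)/2.55 = 55/2.55 = 21.6%. Late weights give (40 + 1.5 × 20)/6.5 = 70/6.5 = 10.8%. The 48-month range is thus about 11 to 24%. Disjoint yearly windows return 40, 20, 0 and 0%.

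- Starting at the plan's 20% (20, 10, 0, 0%), the 48-month figure is 30/4 = 7.5% with equal weights and 27.5/2.55 = 10.8% with declining weights. With late weights it is 35/6.5 = 5.4%.
- In the other direction (0, 20, 40, 40%), the Cox calculation gives 16.5 to 25.2% at 48 months over 0 to 40% yearly disenrolment, against a true year-4 VE of 40%.
- If the fourth window runs to the end of the study, the 40/20/0/0% pattern gives about 8 to 21% over the same disenrolment range.

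**4. Precision of disjoint years.** The SAP's probabilities cover the maximum study period, up to seven years. Spreading the 2,310 events over seven years with 0 to 40% yearly loss leaves about 209 to 923 events in each of the first four years. The formula in step 1 then gives 18.5 to 60.9% power for HR 0.80. With SE = 1/√(events × 0.15 × 0.85), the 95% CI around VE 20% is about −17 to 45% at 209 events and 4 to 33% at 923.

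**The case against.** Cumulative VE through a given month is a legitimate estimand, and SAP 5.3.2 defines it openly. The objective can be read as effect through those times, and only the table heading plainly says year. All of that stands. The fault is the mismatch between label and quantity, and relabelling alone would cure that part.

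A reader might infer that the plan has nothing to detect a changing vaccine effect. The documents do not support this. The proportionality check covers the vaccine term. Unadjusted Kaplan-Meier curves by exposure are planned, with a maximum time of 2,500 days in the appendix code. Table 3.2 shows cases and person-years per window, so crude yearly rates follow by subtraction. What is missing is narrower. There is no adjusted VE per interval. There is also no usable rule if the vaccine term itself is non-proportional, because the exposure cannot be dropped and stratified on when its hazard ratio is the endpoint. SAP 7.2.1.1 mentions a time-varying approach but explains it only through entry and end dates.

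A reader might also infer that the windows always lean towards early follow-up and so overstate durability. They lean wherever the events fall. Equal weights show no early lean, late weights reverse it, and weak early protection would also be carried forward.

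Finally, the study is exploratory and tests no hypothesis, no decision rule rests on Table 3.2, and a reader would see the cumulative figures fall. That limits the urgency.

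**Conclusion.** The point holds as a mismatch between what is asked and labelled and what is estimated. It matters only if VE changes over time. With constant VE the four windows estimate the same hazard ratio, and the analysis adds nothing but does no harm. With changing VE, the rows after the first cannot be read as VE at that month or in that year.

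The sizes in the working rest on assumed VE patterns and assumed spreads of events, and are illustrations only. They show that a year-4 effect of zero could appear as roughly 11 to 24% if VE starts at 40%. If it starts at 20%, the figure is about half that. Nothing in the documents shows that VE for this vaccine does wane.

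Separately, the fourth window ends at the end of the study in SAP 7.2.3.5.1 and protocol 9.7, but at 48 months in SAP 5.3.2 and Table 3.2. These need to be reconciled.

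**What to change.** - Split follow-up at 365, 730, 1095 and 1460 days since zero time and fit the adjusted Cox model with a vaccine-by-interval term. Include interval main effects if the time axis is calendar date, which the entry-date and end-date wording in SAP 7.2.1.1 may imply.
- Report adjusted VE with 95% CI in Table 3.2 for days 14–365, 366–730, 731–1095 and 1096–1460. State whether time after day 1460 forms a further interval or is cut off.
- Keep the cumulative windows as separate rows labelled as effect through month 12, 24, 36 and 48, and correct the table heading.
- Settle whether the fourth window ends at 48 months or at the end of the study, and use that in every section.
- State in SAP 7.2.1.1 that if the vaccine term fails the proportionality check, the interval-specific estimates are reported alongside the overall one.

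This needs no new data, since the planned entry-and-exit data layout already allows follow-up to be split. The cost is some programming and low precision: roughly 19 to 61% power per interval for HR 0.80 under the assumptions above. With no multiplicity adjustment planned ("The alpha level will be 0.05, 2-sided. No adjustments for multiple comparisons will be made"), the interval estimates should be presented as descriptive.

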8.1.3. Exploratory Objectives

- 1. To examine the effect of at least 1 dose of Trumenba on gonococcal infection in adolescents and young adults of 16-23 years in the US.
- 2. To examine the effect of 1 dose of Trumenba on gonococcal infection in adolescents and young adults of 15-30 years in the US at 12 months, 24 months, 36 months and 48 months following the index vaccination.

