9. RESEARCH METHODS

9.1. Study Design

This is a retrospective cohort study using health care administrative claims data as described in Section 9.4 Data Sources.

Adolescents and young adults approximately 15 to 30 years of age at their individual time zero (calculated based on birth year) will be identified from administrative claims during 01 January 2016 and 31 December 2021.

The exposure cohort will be the individuals who have received at least 1 dose of Trumenba and at least 1 dose of MenACWY (Menactra[®], Menveo[®], or MenQuadfi[®]) prior to the Trumenba vaccination, between 01 January 2016 and 31 December 2021. The index date (zero time) for the exposed cohort is the last date of vaccination, and the cohort will be followed from 14 days after vaccination to the end of the study period (31 December 2022). The individuals in the cohort will be censored by the event of interest, death date (if known), plan disenrollment (if known) or the end of the study period, whichever comes first.

PFIZER CONFIDENTIAL CT24-WI-GL02-RF02 4.0 Non-Interventional Study Protocol Template For Secondary Data Collection Study 01-Jun-2022 Page 11 of 22

The reference cohort will be those with at least 1 dose of MenACWY vaccine, but no doses of Trumemba during the observation period, received between 01January 2016 and 31 December 2021. The MenACWY-only vaccinated cohort is used as a reference cohort rather than an unvaccinated cohort in order to help control for theoretical differences in health seeking and risk behaviors between vaccinated and unvaccinated individuals. The index date (zero time) of the reference cohort is the last dose of MenACWY and these individuals will be followed from 14 days after zero time until the earliest occurrence of the following: outcome of interest, death date (if known), plan disenrollment (if known) or 31 December 2022 (end of study period).

The outcomes of interest are gonococcal and chlamydial infections and only the first episode within the study period will be considered as event in case of repeated infections.

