9.7. Data Analysis

The zero time is the date of Trumenba vaccination for the exposed group and the date of MenACWY for the unexposed group. We will assess gonococcal infections that occurred between i) 14 days after zero time and 365 days ii) 14 days after zero time and 730 days, iii) 14 days after zero time and 1095 days, and iv) 14 days after zero time and till end of the study period (31Dec2022). We will censor the data in the event of interest, death date (if known), plan disenrollment (if known), target end date, or the end of the study period, whichever comes first. In descriptive analyses, we will fit Kaplan-Meier curves. We will also create unadjusted and covariate adjusted Cox proportional hazard regression models verifying first that the proportionality assumption was satisfied for all independent variables. Hazard ratios (HRs) will be estimated by exponentiation of the coefficient for the vaccine variable in these models, with vaccine effectiveness estimated as (1–HR)×100%. SEs for the coefficients will be used to estimate p values and CIs for the HRs. If a covariate does not satisfy the assumption of proportionality, we will exclude the variable for the multivariable model and will perform the stratified analysis using the covariate.

Detailed methodology for summary and statistical analyses of data collected in this study will be documented in a statistical analysis plan (SAP), which will be dated, filed and maintained by Pfizer. The SAP may modify the plans outlined in the protocol; any major modifications of primary endpoint definitions or their analyses would be reflected in a protocol amendment.

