2.1 STUDY DESIGN

This is a retrospective cohort study including individuals 15 to 30 years of age enrolled in a health plan covered by IQVIA PharMetrics® Plus during 1 Jan 2016 to until the latest release of the data (October 2022). The study is to estimate the effect of Trumenba vaccination on the disease of interest, in particular, the gonococcal incidences will be compared between the recipients of Trumenba + MenACWY vaccines and the recipients of MenACWY vaccine.

The exposure cohort will be the individuals who have received at least one dose of Trumenba and at least one dose of MenACWY between 1 January 2016 and 31 December 2021. The non–exposure or reference cohort will be the individuals with no dose of Trumenba but at least one dose of MenACWY vaccine received during the same time period.

PFIZER CONFIDENTIAL CT24-WI-GL03-RF03 2.0 Non-Interventional Statistical Analysis Plan For Secondary Data Collection Study 01-Jun-2020 Page 4 of 28 The date of index vaccination (zero time) for the exposed cohort is the date of the last dose of Trumenba vaccination, after at least one dose of MenACWY. Trumemba and MenAWCY will be identified by Current Procedural Terminology® (CPT) codes and National Drug Codes (NDC) listed in Appendix Tables 4 and 3, respectively. The index date of the unexposed cohort is the first date of MenACWY vaccination. The diseases of interest are gonococcal infection and chlamydia infections occurring at least 14 days after the zero time. International Classification of Diseases, Tenth Revision, Clinical Modification (ICD-10-CM) codes listed in Appendix Table 1 and 2 will identify gonococcal and chlamydia infections, respectively. Only the first episode will be considered as the event in case of repeated infections. Individuals will be followed until the earliest occurrence of the following: outcome, at death date (if known), at plan disenrollment or end of study period.

Study population

This is a retrospective cohort study and the study population are adolescents and young adults approximately 15 to 30 years of age at their date of vaccination (calculated based on birth year) and will be identified from administrative claims during 01 January 2016 and 31 December 2021.

Data source

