5.3.2 Exploratory Endpoints

 VE calculated as 1 minus the hazard ratio for gonococcal infection between the recipients (aged 16-23 years) of both Trumenba (at least one dose) and MenACWY (at least one dose) vaccines and the recipients (aged 16-23 years) of MenACWY vaccine only multiplied by 100, adjusted for potentially confounding variables (age, sex, and US region, as appropriate).

In this analysis, the cases are those who had at least one claim of gonococcal infection in the database. Each individual will be followed until the end of the follow-up period, censoring the follow-up at death date (if known) or plan disenrollment (if known).

PFIZER CONFIDENTIAL

CT24-WI-GL03-RF03 2.0 Non-Interventional Statistical Analysis Plan For Secondary Data Collection Study 01-Jun-2020 Page 10 of 28 2. VE calculated as 1 minus the hazard ratio for gonococcal infection between the recipients (aged 15-30 years) of both Trumenba (at least one dose) and MenACWY (at least one dose) vaccines and the recipients (aged 15-30 years) of MenACWY vaccine only multiplied by 100, adjusted for potentially confounding variables (age,sex, and US region).

In this analysis, the cases are those who had at least one claim of gonococcal infection in the database. Each individual will be followed for the outcome from 14 days after their zero time until the end of the follow-up period, censoring the follow-up at death date (if known) or plan disenrollment (if known).

The analysis will be carried out by different periods of study (zero time to 12 months post zero time, zero time to 24 months post zero time, zero time to 36 months post zero time, and zero time to 48 months post zero time)

Variable	Role	Operational definition
Age (years)	Baseline characteristic and potential confounder	Age will be calculated based on the 1 st date of Trumenba vaccination for the exposed cohort and the date of the 1 st dose of MenACWY for the unexposed cohort
Sex	Baseline characteristic and potential confounder	Sex will be categorized as female and male
US region	Baseline characteristic and potential confounder	US region which is categorized as : E=Northeast S=South MW=Midwest W=West

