7.2.1.1 Primary Endpoint - Main Analysis

Vaccination Status

If a participant received at least one dose of Trumenba and at least one dose of MenACWY vaccine will be considered as vaccinated (exposed population).

Analysis

We will assess gonococcal infection that occurred between 14 days after zero time and till end of the study period. We will censor the data at death date (if known), plan disenrollment, or the end of the study period, whichever comes first. In descriptive analyses, we will fit Kaplan-Meier curves. We will also create unadjusted and covariate adjusted Cox proportional hazard regression models with time varying approach verifying first that the proportionality assumption was satisfied for all independent variables. Since the individuals entered into the surveillance at different points of time, we will employ the computing process algorithm of the proportional hazard model where the date of entry and the date of end of follow-up will be used in the model instead of time contribution to compute the hazard ratios.

Hazard ratios (HRs) will be estimated by exponentiation of the coefficient for the vaccine variable in these models, with vaccine effectiveness estimated as $(1-HR)\times100\%$. Standard errors (SEs) for the coefficients will be used to estimate p-values and 95% CIs for the HRs. If a covariate does not satisfy the assumption of proportionality, we will exclude the variable for the multivariable model and will perform the stratified analysis using the covariate. Both crude and adjusted VE with its corresponding 95% CI will be calculated.

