10.2 APPENDIX 2: ADDITIONAL STATISTICAL METHODOLOGY DETAILS

10.2.1 Procudure for producing the KM Curve

Proc lifetest data=ana outtest=test maxtime=2500 outsurv=surv noprint; time time*event(0); strata exposure/test=logrank;run; symbol1 i=join c=black v=none; symbol2 i=join c=red v=none; title h=1 "Kaplan-Meier Survival Curve of Not Having Gonoccoal Infection"; proc gplot data=surv; plot survival*time=exposure; run;

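### The 48-month exploratory vaccine effectiveness has no 48-month window in SAP 7.2.3.5.1: the fourth window runs to end of study and would repeat the primary gonococcal estimate under a 48-month label

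*SAP*

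**What the plan says.** Four places set the last horizon of exploratory endpoint 2 at 48 months:

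- Protocol 8.1.3, objective 2, wants the effect "at 12 months, 24 months, 36 months and 48 months following the index vaccination".
- SAP 2.2.3 names the same four horizons.
- SAP 5.3.2 lists the analysis periods, ending with "and zero time to 48 months post zero time".
- The Table 3.2 shell in SAP 8.3 has a fourth block labelled 48 months of follow-up.

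SAP 7.2.3.5.1, the analysis section for this endpoint, gives days 365, 730 and 1,095 as the ends of the first three windows, then "iv) 14 days after zero time and till end of the study period". It takes everything else from SAP 7.2.1.1. SAP 4.4 also sends the reader to 7.2.3.5.1 for the time points.

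The primary analysis in SAP 7.2.1.1 reads: "We will assess gonococcal infection that occurred between 14 days after zero time and till end of the study period".

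Protocol 9.7 lists the same four windows as SAP 7.2.3.5.1, with the fourth ending on 31 December 2022.

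**The concern.** The first three windows agree with their labels and the fourth does not. Nothing in either document equates end of study with 48 months. One programmer working from SAP 5.3.2 and another from SAP 7.2.3.5.1 would fill the last block of Table 3.2 with different numbers.

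The four horizons are there so that VE can be compared across lengths of follow-up. If 7.2.3.5.1 is followed, the last row uses all available follow-up, and a reader would take it as a 48-month result. The row would also add no information, because it would be the primary at-least-one-dose gonococcal estimate printed a second time.

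**Working it through.** **Step 1. Is window iv the same analysis as the primary?**

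| Item | Primary (SAP 5.1.1, 7.2.1.1) | Exploratory 2, window iv (SAP 5.3.2, 7.2.3.5.1) |
|---|---|---|
| Population | age 15-30 | age 15-30 |
| Exposed | at least one Trumenba and one MenACWY dose | same |
| Outcome | gonococcal infection | same |
| Start | day 14 | day 14 |
| End | end of study | end of study |
| Model, censoring | Cox, as in 7.2.1.1 | by reference to 7.2.1.1 |
| Covariates | age, sex, US region | same |

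Every item agrees, so the estimates, crude and adjusted, would be identical. This rests on the SAP wording. Protocol 8.1.3 says one dose where SAP 2.2.3 says at least one, so the duplication cannot be read from the protocol alone.

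**Step 2. How far is end of study from 48 months?** The earliest index date is 1 January 2016 (protocol 9.1, SAP 2.1). Continuing the SAP's 365-day pattern, 48 months is 4 × 365 = 1,460 days. Months below are days / 30.4375.

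- To 31 December 2022 (protocol 9.1): 2,556 days = 84.0 months.
- To 31 October 2022 (SAP 2.1 gives only the month): 2,495 days = 82.0 months.
- To 1 October 2022: 2,465 days = 81.0 months.

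The Kaplan-Meier code in SAP 10.2.1, "Proc lifetest data=ana outtest=test maxtime=2500", stops at 2,500 days, or 82.1 months. That is 2,500 − 1,460 = 1,040 days past the 48-month point. The code serves the figures and does not govern this endpoint, but it shows that follow-up beyond day 1,460 was expected.

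**Step 3. How much follow-up lies past day 1,460?** The documents give neither the spread of index dates nor the rate of disenrolment, so both are assumed. Index days run over 1 January 2016 to 31 December 2021 (2,192 days). Disenrolment is exponential with rate h = 1/(mean enrolment in years × 365.25). Someone with potential follow-up f contributes

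PT(f) = [exp(−14h) − exp(−fh)] / h,

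or f − 14 with no disenrolment. The share beyond day 1,460 is 1 − Σw·PT(min(f, 1,460)) / Σw·PT(f), where w is the weight of each index day.

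Check by hand for uniform index dates, no disenrolment and an end date of 31 December 2022. Here f runs from 365 to 2,556, so mean person-time is (365 + 2,556)/2 − 14 = 1,446.5 days. Of the index days, 1,096/2,192 = 50% allow f > 1,460, with mean excess (1 + 1,096)/2 = 548.5 days. The share is 0.5 × 548.5 / 1,446.5 = 19.0%.

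Ranges cover the three end dates above:

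| Assumed index dates | Index dates allowing > 1,460 days | Mean enrolment 1 y | 2 y | 4 y | No disenrolment |
|---|---|---|---|---|---|
| Uniform | 46-50% | 0.6-0.7% | 3.7-4.1% | 8.3-9.3% | 17.0-19.0% |
| Rising linearly from zero | 21-25% | 0.2-0.3% | 1.4-1.7% | 3.3-3.9% | 7.1-8.5% |

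The last four columns are shares of person-time. The second row illustrates later index dates. Protocol section 7 reports rising MenB coverage, which makes later dates plausible for the exposed cohort, but it does not give this distribution.

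**The case against.** The strongest reply is about weight. The endpoint is exploratory, no hypothesis is tested, and no primary or power figure changes. Most places in the SAP, including the shell the programmer fills, say 48 months, so a careful programmer might apply the cap anyway. If not, the number printed would be a valid end-of-study VE with the wrong label. With mean enrolment of one or two years, the person-time at issue is only 0.2% to about 4%. The 17-19% figure needs nobody to disenrol over up to seven years.

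All of that stands as a limit on the consequence. The person-time table shows a range of possibilities and does not demonstrate a material shift in VE. The linear scenario is weakly supported: the coverage figures concern any MenB vaccine, are levels rather than yearly counts of new index dates, and say nothing about the MenACWY-only cohort, roughly 85% of subjects (SAP section 3).

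It does not remove the contradiction. The section at odds with the rest is the one that tells the programmer what to run, and SAP 4.4 points to it. The mislabelled row would be there whatever the size of the shift.

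It is also fair to say that a protocol edit is not strictly required. Protocol 9.7 and SAP section 2 let the SAP modify the protocol, and they ask for an amendment only for major changes to the primary endpoint or its analysis. The end-of-study window in protocol 9.7 is not wrong in itself: that section covers all the analyses, and it is the only window there that serves the primary. What is missing is a 48-month window beside it.

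**Conclusion.** The point holds. SAP 7.2.3.5.1 contradicts SAP 2.2.3, SAP 5.3.2 and Table 3.2. If programmed as written, it would put the primary at-least-one-dose gonococcal estimate in the 48-month row, with follow-up of up to 81 to 84 months. That conclusion needs only the text and the calendar.

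The share of person-time wrongly included depends on the assumed index dates and disenrolment, and the effect on VE is unknown. The reach is one exploratory time point; the primary endpoint and the stated power are untouched. It should be corrected before the analysis is programmed, but it does not threaten the study's main result.

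**What to change.** In SAP 7.2.3.5.1, end window iv at day 1,460, so that it agrees with SAP 2.2.3, SAP 5.3.2 and Table 3.2. Report end-of-study VE only as the primary analysis.

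In protocol 9.7, preferably add a window from day 14 to day 1,460 to match objective 2 in 8.1.3, and keep the existing end-of-study window for the primary.

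The alternative is to relabel the fourth time point as end of study in protocol 8.1.3, SAP 2.2.3, SAP 5.3.2 and Table 3.2. That is also consistent, but it changes more text and leaves a row that duplicates Table 2.1.

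The cost of the preferred route is one extra censoring date in the program, one SAP edit and one added line in the protocol, with no new data.
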